## Protocol Summary

**Study Compound:** Atogepant

---

**Phase:** 3

---

**Study Objective:**

To evaluate the safety and tolerability of treatment with atogepant 60 mg once daily for the prevention of migraine over a 40-week duration.

---

**Clinical Hypotheses:**

Atogepant 60 mg once daily is safe and well tolerated when administered over 40 weeks

---

**Study Design**

---

*Structure:* Multicenter, open-label, 40-week, long-term safety extension study conducted in the United States

*Duration:* The study will consist of a 40-week treatment period, and a safety follow-up period of an additional 4 weeks, for a total duration of 44 weeks.

*Study Intervention:* Atogepant 60 mg once daily

*Control:* Not applicable

*Dosage/Dose Regimen:* Atogepant 60 mg once daily will be administered for 40 weeks.

*Randomization:* Not applicable

*Visit Schedule:* Participants will directly rollover from Study 3101-301-002 (Phase 3 episodic migraine [EM]). As such, participants will have Visit 7 from Study 3101-301-002 function as the Visit 1 for this study after the participant signs the informed consent. After Visit 1, study visits will occur every 4 weeks for the duration of the study. An End of Study (EOS) Visit will occur 4 weeks after the last dose of atogepant. During the COVID-19 pandemic, Visit 12 (Follow-up/End of Study) should be conducted remotely for all participants.

Note, there may be participants who complete Visit 7 in the lead-in Study 3101-301-002 before extension Study 3101-309-002 has been initiated. Those participants should complete Visit 7/ET and Visit 8/EOS Visit (including discontinuation of IP) per the Study 3101-301-002 Schedule of Visits and Procedures.

Depending on the timing of the initiation of this extension study in relation to each participant's planned Visit 8 schedule, Visit 1 Study 3101-309-002 can be conducted on the same day as Visit 8/EOS Visit for Study 3101-301-002 or soon thereafter.

- If this extension study is initiated prior to the participant's planned Visit 8 in the lead-in study, then Visit 8/EOS Visit for Study 3101-301-002 should be conducted on the same day as Visit 1 for Study 3101-309-002.
- If this extension study is not initiated prior to the participant's planned Visit 8 in the lead-in study (ie, there is a gap between Visit 8 and Visit 1), then Visit 8/EOS Visit should be conducted as planned per the Study 3101-301-002 Schedule of Visits and Procedures. When this extension study is initiated, the participant should return to the clinic as soon as possible, and Visit 1 should be conducted per the Study 3101-309-002 Schedule of Visits and Procedures.

For details, please see [Table 1](#), the Schedule of Visits and Procedures.

**Study Population Characteristics**

*Number of Participants/Sites:* All participants who complete Study 3101-301-002, and meet all eligibility requirements, may participate in this study. Based on expected completion rates from Study 3101-301-002, it is estimated that approximately 750 participants will be enrolled from approximately 110 centers in the United States.

*Condition/Disease:* Migraine with aura or migraine without aura (ICHD-3 Section 1.1 or Section 1.2)

*Inclusion Criteria:*

- Written informed consent and participant privacy information (eg, written authorization for use and release of health and research study information) obtained from the participant prior to initiation of any study-specific procedures.
- Participants must be using a medically acceptable and effective method of birth control during the course of the entire study, as defined in [Section 4.4.3](#).
- Eligible participants who completed the double-blind treatment period (Visit 7) and the follow-up period Visit 8, if applicable depending on the timing of study initiation, of Study 3101-301-002 without significant protocol deviations (eg, noncompliance to protocol-required procedures) and who did not experience an adverse event (AE) that, in the investigator's opinion, may indicate an unacceptable safety risk.

*Key Exclusion Criteria:*

- Participants with clinically significant hematologic, endocrine, cardiovascular, pulmonary, renal, hepatic, gastrointestinal, or neurologic disease.

**Response Measures**

*Safety* – AEs, physical examinations, clinical laboratory determinations, vital sign measurements, electrocardiogram (ECG) parameters, and the Columbia-Suicide Severity Rating Scale (C-SSRS)

*Efficacy* – Not applicable

[figure not shown]
**General Statistical Methods and Types of Analyses:**

The safety parameters will include AEs, clinical laboratory determinations, vital sign measurements, ECG parameters, and the C-SSRS. For each of the clinical laboratory determinations, vital sign measurements, and ECG parameters, the last non-missing safety assessment before the first dose of treatment will be used as the baseline for all analyses of that safety parameter. For all participants, baseline in lead-in study (Study 3101-301-002) will be used. Continuous variables will be summarized by the number of participants and mean, standard deviation (SD), median, minimum, and maximum values. Categorical variables will be summarized by number and percentage of participants.

*Sample Size Calculation:*

As this is a safety extension study, all eligible participants from lead-in Study 3101-301-002 may be enrolled.

**Figure 1.** Study Diagram

ET = early termination; V = visit; Wk = week.

**Table 1. Schedule of Visits and Procedures for In-person Visits Conducted Prior to or During the COVID-19 Pandemic**

Study Period	Open-label Treatment Period (40 weeks)										Safety Follow-up Period (4 weeks)	
	Visit 1 a	Visit 2	Visit 3	Visit 4	Visit 5	Visit 6	Visit 7	Visit 8	Visit 9	Visit 10	Visit 11/ET	Visit 12/ EOS e
Day/Week	Week 4 (Day 28)	Week 8 (Day 56)	Week 12 (Day 84)	Week 16 (Day 112)	Week 20 (Day 140)	Week 24 (Day 168)	Week 28 (Day 196)	Week 32 (Day 224)	Week 36 (Day 252)	Week 40 (Day 280)	Week 44 (Day 308)	
Visit Windows	± 3 days	± 3 days	± 3 days	± 3 days	± 3 days	± 3 days	± 3 days	± 3 days	± 3 days	± 3 days	± 3 days	
Obtain Informed Consent and participant privacy	X											
Access IWRs	X	X	X	X	X	X	X	X	X	X	X	
Assess inclusion/exclusion criteria	X											
Perform physical examination	X											
Collect vital sign measurements b	X	X	X	X	X	X	X	X	X	X	X	
Perform ECG	X											
Perform urine pregnancy test c	X	X	X	X	X	X	X	X	X	X	X	
Clinical laboratory determinations d	X	X	X	X	X	X	X	X	X	X	X	
C-SSRS	X	X	X	X	X	X	X	X	X	X	X	
Dispense study intervention (ie, atogepant)	X	X	X	X	X	X	X	X	X	X	X	
Review of study intervention (ie, atogepant) compliance and accountability	X	X	X	X	X	X	X	X	X	X	X	
Adverse Events	X	X	X	X	X	X	X	X	X	X	X	
Concomitant medications/concurrent procedures	X	X	X	X	X	X	X	X	X	X	X	

C-SSRS = Columbia Suicide Severity Rating Scale; ECG = electrocardiogram; EOS = end of study; ET = early termination; INR = international normalized ratio; IWRs = interactive web response system.

a After providing informed consent for the current study, Visit 1 will be conducted on the same day as Study 3101-301-002 Visit 7; procedures collected as part of Study 3101-301-002 Visit 7 should not be repeated. Visit 1 must be conducted as an in-person visit.

b Vital sign measurements: Weight, sitting and standing pulse rate, respiratory rate, sitting and standing blood pressure, and body temperature.

c For women of child-bearing potential only, a urine pregnancy test will be performed at all visits.

d Clinical laboratory determinations include chemistry, hematology, coagulation parameters (INR), and urinalysis to be collected for all visits. Samples for serology and the urine drug screen will be collected only at screening (Visit 1).

e During the COVID-19 pandemic, Visit 12 (Follow-up/End of Study) should be conducted remotely for all participants.

**Table 2. Schedule of Visits and Procedures for Visits Conducted Remotely Due to the COVID-19 Pandemic**

Study Period	Open-label Treatment Period (40 weeks) a										Safety Follow-up Period (4 weeks)
	Visit #	Visit 2	Visit 3	Visit 4	Visit 5	Visit 6	Visit 7	Visit 8	Visit 9	Visit 10	
Day/Week	Week 4 (Day 28)	Week 8 (Day 56)	Week 12 (Day 84)	Week 16 (Day 112)	Week 20 (Day 140)	Week 24 (Day 168)	Week 28 (Day 196)	Week 32 (Day 224)	Week 36 (Day 252)	Week 40 (Day 280)	Week 44 (Day 308)
Visit Windows	± 3 days	± 3 days	± 3 days	± 3 days	± 3 days	± 3 days	± 3 days	± 3 days	± 3 days	± 3 days	± 3 days
Access IWRS	X	X	X	X	X	X	X	X	X	X	X
Provide urine pregnancy test and instructions b	X	X	X	X	X	X	X	X	X	X	X
C-SSRS	X	X	X	X	X	X	X	X	X	X	X
Dispense study intervention (ie, atogepant)	X	X	X	X	X	X	X	X	X	X	X
Review of study intervention (ie, atogepant)	X	X	X	X	X	X	X	X	X	X	X
Compliance and accountability	X	X	X	X	X	X	X	X	X	X	X
Adverse Events											
Concomitant medications/concurrent procedures	X	X	X	X	X	X	X	X	X	X	X

C-SSRS = Columbia Suicide Severity Rating Scale; ECG = electrocardiogram; EOS = end of study; IWRS = interactive web response system.

a For participants who have a study visit replaced by a remote study visit, all missed in-person safety assessments (clinical laboratory determinations, vital signs, and ECGs) will be collected at the next in-person visit. To ensure participant safety, remote study visits can be performed for up to 8 weeks at the discretion of the investigator, after which, participants who cannot attend in-person for a study visit must be discontinued from the study.

b For women of childbearing potential only, a urine pregnancy test must be performed within 48 hours prior to the remote visits. Investigators/site staff will provide participants with study-supplied urine pregnancy tests and corresponding written instructions to be used at home by participants for remote study visits. Sites are required to verbally review testing instructions with all participants.

c During the COVID-19 pandemic, Visit 12 (Follow-up/End of Study) should be conducted remotely for all participants.

## 1 Background and Clinical Rationale

### 1.1 Background

Migraine affects 18% of women and 6% of men in the United States with peak prevalence occurring between the ages of 25 and 55 years. Approximately one-third of patients with migraines have 3 or more migraine attacks per month, and over half report severe impairment or the need for bed rest (Lipton 2007). In the United States alone, work loss due to migraine is estimated to cost ~ \$13 billion annually (Hu 1999). Prevalence is similar in Europe, with migraine headache affecting on average 17.6% of women and 8% of men (Stovner 2010). The Global Burden of Disease Survey 2010 (Vos 2013) estimated the global prevalence of migraine to be 14.7%, making it the third most common disease in the world in both males and females. Migraine was ranked seventh highest among specific causes of disability globally (Steiner 2013).

Migraine is typically characterized by attacks of throbbing, unilateral headache of moderate or severe pain intensity, associated with nausea, vomiting, and/or sensitivity to light (photophobia) and sound (phonophobia). In about 25% of individuals, the migraine headache is preceded by focal neurological dysfunction (aura). Improving diagnosis and optimizing treatments for migraine have been recognized as critically important to overcoming current barriers to reduce the global burden of migraine.

Because there are no biological markers for migraine, diagnosis is based on clinical history, examination, and the exclusion of other headache disorders. Physicians apply clinical criteria to guide diagnoses and subsequent treatment. EM is a syndrome diagnosis applied to patients with migraine (with or without aura) who have 1 to 14 headache days per month. CM is a specific ICHD-3 diagnosis applied to a subset of patients with  $\geq 15$  headache days per month (Katsarava 2012; Olesen 2004; ICHD-3 2018). This study will evaluate the safety and tolerability of atogepant in participants with migraine.

### 1.2 Overview of Atogepant

Atogepant is a potent, selective oral CGRP receptor antagonist being developed for migraine prevention. Additional information on non-clinical pharmacology, toxicology, and PK properties of atogepant can be found in the IB.

A Phase 2/3 clinical study was conducted, which compared atogepant 10 mg once daily, atogepant 30 mg once daily, atogepant 30 mg BID, atogepant 60 mg once daily and atogepant 60 mg BID to placebo. Overall, all the atogepant doses tested were well tolerated. For the primary efficacy endpoint of change from baseline in mean monthly migraine days across the

12-week treatment period, all atogepant doses demonstrated a statistically significant reduction compared with placebo in participants with EM.

### **1.3 Study Rationale**

The purpose of this study is to evaluate the safety and tolerability of atogepant 60 mg once daily, when taken for 40 weeks for the prevention of EM.

### **1.4 Rationale for Doses and Dose Regimens Selected**

The Phase 3 pivotal studies to evaluate atogepant will test a maximum dose of 60 mg once daily. For this reason, the same dose of 60 mg once daily has been selected for this study to evaluate the long-term safety and tolerability of atogepant for the prevention of EM.

## **2 Study Objective and Clinical Hypotheses**

### **2.1 Study Objective**

To evaluate the safety and tolerability of treatment with atogepant 60 mg once daily when administered over 40 weeks for the prevention of migraine in participants with EM.

### **2.2 Clinical Hypothesis**

Atogepant 60 mg once daily is safe and well tolerated when administered over 40 weeks for the prevention of migraine in participants with EM.

## **3 Study Design**

### **3.1 Structure**

This is a multicenter, open-label, 40-week, long-term safety extension study conducted in the United States and will enroll approximately 750 participants from approximately 110 sites. Participants will be treated with atogepant 60 mg once daily.

The study will consist of a 40-week open-label treatment period, and a safety follow-up period of 4 weeks.

Participants will directly rollover from Study 3101-301-002 (Phase 3 EM). As such, participants will have Visit 7 from Study 3101-301-002 function as the Visit 1 for this study after the participant signs the informed consent. After Visit 1, study visits will occur every 4 weeks for the duration of the study. An EOS Visit will occur 4 weeks after the last dose of atogepant.

Note, there may be participants who complete Visit 7 in the lead-in Study 3101-301-002 before extension Study 3101-309-002 has been initiated. Those participants should complete Visit 7/ET and Visit 8/EOS Visit (including discontinuation of study intervention) per the Study 3101-301-002 Schedule of Visits and Procedures.

Depending on the timing of the initiation of this extension study, in relation to each participant's planned Visit 8 schedule, Visit 1 Study 3101-309-002 can be conducted on the same day as Visit 8/EOS Visit for Study 3101-301-002 or soon thereafter.

- If this extension study is initiated prior to the participant's planned Visit 8 in the lead-in study, then Visit 8/EOS Visit for Study 3101-301-002 should be conducted on the same day as Visit 1 for Study 3101-309-002.
- If this extension study is not initiated prior to the participant's planned Visit 8 in the lead-in study (ie, there is a gap between Visit 8 and Visit 1), then Visit 8/EOS Visit should be conducted as planned per the Study 3101-301-002 Schedule of Visits and Procedures. When this extension study is initiated the participant should return to the clinic as soon as possible, and Visit 1 should be conducted per the Study 3101-309-002 Schedule of Visits and Procedures.

After Visit 1, study visits will occur every 4 weeks for the duration of the 40-week treatment period. Participants will return to the clinic for safety assessments at 4, 8, 12, 16, 20, 24, 28, 32, 36 and 40 weeks relative to Visit 1 (Day 1). An EOS Visit will occur 4 weeks after the last dose of atogepant 60 mg once daily. During the COVID-19 pandemic, Visit 12 (Follow-up/End of Study) should be conducted remotely for all participants. For the schedule of visits and procedures conducted in-person, see [Table 1](#).

To eliminate immediate potential hazards to participants and study staff due to the COVID-19 pandemic while ensuring participant safety and maintaining data integrity, the protocol has been updated to allow investigators/appropriately designated study staff to perform study visits remotely. For the schedule of visits and procedures conducted remotely, see [Table 2](#).

The primary objective of the study is to assess the safety and tolerability of long-term atogepant treatment. The planned safety assessments include collection of AEs, clinical laboratory determinations, ECGs, vital sign measurements, physical examinations, and the C-SSRS.

### **3.2 Data Safety Monitoring Board**

An independent DSMB will be established to review safety data and summary reports, identify any safety issues and trends, and make recommendations to Allergan, including modification or ET of a trial, if emerging data show unexpected and clinically significant AEs.

Details of the DSMB memberships, standard operational procedures for data monitoring/review, frequency of review, and other pertinent details will be provided in a separate DSMB Charter.

### **3.3 Adjudication Committee**

An Adjudication Charter will be established and will describe the process for the surveillance, monitoring, and adjudication by the Clinical Adjudication Committee of events of post-treatment elevations of ALT and/or AST  $\geq 3 \times$  ULN. The purpose of this charter will be to provide a standardized process for the adjudication of the events in order to determine whether the elevation was related to atogepant.

## **4 Study Population and Entry Criteria**

### **4.1 Number of Participants**

Approximately 750 participants will be treated with atogepant 60 mg once daily at approximately 110 centers in the United States.

### **4.2 Inclusion Criteria**

1. Written informed consent and participant privacy information (eg, written authorization for use and release of health and research study information) obtained from the participant prior to initiation of any study-specific procedures.
2. Participants must be using a medically acceptable and effective method of birth control during the course of the entire study, as defined in [Section 4.4.3](#).
3. Eligible participants who completed the double-blind treatment period (Visit 7) and the follow-up period (Visit 8), if applicable, depending on the timing of study initiation, of Study 3101-301-002 without significant protocol deviations (eg, noncompliance to protocol-required procedures) and who did not experience an AE that, in the investigator's opinion, may indicate an unacceptable safety risk.

### 4.3 Exclusion Criteria

1. Requirement for any medication, diet (ie, grapefruit juice), that is on the list of prohibited concomitant medications (see [Section 4.4.2](#) and [Attachment 12](#)) that cannot be discontinued or switched to an allowable alternative medication. This includes concomitant medications with demonstrated efficacy for the prevention of migraine (eg, amitriptyline, topiramate, propranolol).
2. Female participant is pregnant, planning to become pregnant during the course of the study, or currently lactating. Women of childbearing potential must have a negative urine pregnancy test at Visit 1.
3. An ECG with clinically significant abnormalities at Visit 1 as determined by the investigator.
4. Hypertension as defined by sitting systolic BP > 160 mm Hg or sitting diastolic BP > 100 mm Hg at Visit 1. Vital sign measurements that exceed these limits may be repeated only once.
5. Significant risk of self-harm based on clinical interview and responses on the C-SSRS, or of harm to others in the opinion of the investigator; participants must be excluded if they report suicidal ideation with intent, with or without a plan, (ie, Type 4 or 5 on the C-SSRS) since the last visit.
6. Participants with clinically significant hematologic, endocrine, cardiovascular, pulmonary, renal, hepatic, gastrointestinal, or neurologic disease.
7. Participant has a condition or is in a situation which in the investigator's opinion may put the participant at significant risk, may confound the study results, or may interfere significantly with participation in the study.
8. Any medical or other reasons (eg, unlikely to adhere to the study procedures, keep appointments, or is planning to relocate during the study) that, in the investigator's opinion, might indicate that the participant is unsuitable for participation in the study.

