### **6.5.7 Columbia-Suicide Severity Rating Scale (C-SSRS)**

The C-SSRS is a clinician-rated instrument that reports the severity of both suicidal ideation and behavior. Suicidal ideation is classified on a 5-item scale: 1 (wish to be dead), 2 (nonspecific active suicidal thoughts), 3 (active suicidal ideation with any methods [not plan] without intent to act), 4 (active suicidal ideation with some intent to act, without specific plan), and 5 (active suicidal ideation with specific plan and intent). The C-SSRS also captures information about the intensity of ideation, specifically the frequency, duration, controllability, deterrents, and reasons for the most severe types of ideation. Suicidal behavior is classified on a 5-item scale: 0 (no suicidal behavior), 1 (preparatory acts or behavior), 2 (aborted attempt), 3 (interrupted attempt), and 4 (actual attempt). More than 1 classification can be selected provided they represent separate episodes. For actual attempts only, the actual or potential lethality is classified for the initial, most lethal, and most recent attempts. The C-SSRS will be completed at all study visits. At all visits the C-SSRS will be completed for ideation and behavior since last visit for all participants. The C-SSRS will be completed by the investigator or designee with current and valid training in administering the assessment. A participant should not be released from the study center until the results of C-SSRS are reviewed and it is confirmed that the participant is

not considered to be at risk. Participants who reply with “yes” to questions 4 or 5 in the suicidal ideation section or “yes” to any question in the suicidal behavior section of the C-SSRS at Visits 2 through 10 must be withdrawn from the study and should receive appropriate follow-up as in routine clinical practice, including the ET (Visit 11) and the EOS (Visit 12) visits.

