## 8.9 Withdrawal Criteria

- **Participants with the following at Visit 1:**
  - **Laboratory Results:**
    - ALT or AST > 1 x ULN OR
    - total bilirubin > 1 x ULN (except for participants with a diagnosis of Gilbert's disease) OR
    - serum albumin < 2.8 g/dL
    - Positive result on the urine drug screen unless explained by concomitant medication use (eg, opioids prescribed for migraine pain).
    - Positive result on anti-hepatitis A IgM antibody, hepatitis B surface antigen, anti-hepatitis C antibody testing, or anti-hepatitis E IgM antibody.
  - **ECG Results:**
    - QTcF > 450 msec for males and QTcF > 470 msec for females on the final central vendor ECG report
    - Clinically significant cardiac rhythm or conduction abnormalities (eg, atrial fibrillation, second- or third-degree heart block)
- **Participants with the following at any study visit:**
  - Female participants who become pregnant ([Section 9.4](#))
  - Participants who meet atogepant discontinuation criteria related to abnormal liver function tests ([Section 9.5](#)), and advised not to be rechallenged, will be withdrawn from the study and should refrain from taking atogepant.
  - Participants who reply with “yes” to questions 4 or 5 in the suicidal ideation section or “yes” to any question in the suicidal behavior section of the C-SSRS at Visits 2 through 10 must be withdrawn from the study.
  - A participant with a condition and/or a situation that, in the investigator's opinion, may put the participant at significant risk, may confound the study results, or may interfere significantly with the participant's participation in the study may be withdrawn from treatment.

All withdrawn participants should receive appropriate follow-up as in routine clinical practice, including the ET (Visit 11) and the EOS (Visit 12) assessments.

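### Suicidal behaviour reported at Visit 1 does not automatically exclude a participant, although the same answer at Visits 2 to 10 requires withdrawal

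*Protocol*

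**What the plan says.** Criterion 5 in Protocol 4.3 has two limbs. The first depends on an assessment of risk: "Significant risk of self-harm based on clinical interview and responses on the C-SSRS". The second is compulsory and limited to ideation: "participants must be excluded if they report suicidal ideation with intent, with or without a plan, (ie, Type 4 or 5 on the C-SSRS"), reported since the last visit. Criteria 7 and 8 add general discretion. Criterion 7 concerns a condition or situation "which in the investigator's opinion may put the participant at significant risk", and criterion 8 covers reasons that in the investigator's opinion "might indicate that the participant is unsuitable for participation in the study".

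The C-SSRS collects more than ideation. Section 6.5.7 grades behaviour as "0 (no suicidal behavior), 1 (preparatory acts or behavior), 2 (aborted attempt), 3 (interrupted attempt), and 4 (actual attempt"), and states: "At all visits the C-SSRS will be completed for ideation and behavior since last visit for all participants". Behaviour is therefore on the form at Visit 1.

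After entry the rule is wider. Under 6.5.7 and 8.9, a yes to ideation question 4 or 5, or "to any question in the suicidal behavior section of the C-SSRS at Visits 2 through 10 must be withdrawn from the study". The separate Visit 1 list in 8.9 contains laboratory and ECG results and no C-SSRS item.

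**The concern.** At Visit 1 the site holds a C-SSRS answer on behaviour, and atogepant is dispensed the same day (8.4.1.1). A participant who reports an aborted, interrupted or actual attempt without Type 4 or 5 ideation meets no automatic bar to receiving drug. The outcome depends on how the investigator weighs the risk. The same answer at any of the next nine visits has one fixed consequence.

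The narrower wording looks like an omission. The definition of adverse events of special interest in 6.5.2 puts any suicidal behaviour beside Type 4 or 5 ideation, and so does the withdrawal rule. Only criterion 5 drops the second half, and no reason is given. Other Visit 1 risks have fixed limits: sitting blood pressure above 160 systolic or 100 diastolic mm Hg (4.3), ALT or AST above 1 × ULN, and QTcF above 450 msec in men or 470 msec in women (8.9). An ALT marginally above normal has a set consequence; a reported suicide attempt does not.

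What is at stake is consistent handling of a serious safety signal across about 110 sites.

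**Working it through.** The plan gives no figure to reproduce, so the check sets the rules side by side and counts.

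**Inputs.** Classifications: 6.5.7. Compulsory rule at Visit 1: 4.3, criterion 5. Compulsory rule at Visits 2 to 10: 6.5.7 and 8.9. Visit structure: 8.4.

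| C-SSRS finding | Number of types | Visit 1 | Visits 2 to 10 |
|---|---|---|---|
| Ideation 1 to 3 | 3 | judgement | judgement |
| Ideation 4 or 5 | 2 | automatic exclusion | automatic withdrawal |
| Behaviour 1 to 4 | 4 | judgement | automatic withdrawal |

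**Count of triggers.**
- Positive classifications: 5 ideation + 4 behaviour = 9.
- Automatic at Visit 1: 2 of 9, with 0 of the 4 behaviour types.
- Automatic at Visits 2 to 10: 2 + 4 = 6 of 9.
- Difference: 6 − 2 = 4, all of them behaviour types.

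**Count of visits.** Treatment runs in ten 4-week intervals (10 × 4 = 40 weeks), which begin at Visits 1 to 10. The automatic behaviour rule applies at Visits 2 to 10, so at 9 of the 10. The exception is Visit 1.

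**Does the later rule close the gap?** No. Each form covers only the period since the previous visit. Behaviour already reported at Visit 1 lies outside the period that the Visit 2 form asks about, so the compulsory rule at Visit 2 would not pick it up.

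**Does another section supply the rule?** No.
- Section 8.3 makes the exclusion criteria binding at Visit 1, but a judgement-based criterion binds only once the investigator judges it met.
- The any-visit clause in 8.9 for participants at significant risk rests on the investigator's opinion and permits withdrawal without requiring it.
- Inclusion criterion 3 bars participants with an adverse event that, in the investigator's opinion, may signal unacceptable risk. That too is judgement.
- Sections 6.5.2 and 9.5 impose reporting duties and do not decide entry.

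**The case against.** The strongest reply is that this is a difference in drafting with several layers of cover. The first limb of criterion 5 takes C-SSRS responses as an express input, and those include the behaviour answers. The phrase about the investigator's opinion in that limb can be read as attaching only to harm to others. Criteria 7 and 8, inclusion criterion 3 and the any-visit clause in 8.9 add further routes to exclusion or withdrawal. Visit 1 must be in person (Table 1, footnote a), and section 6.5.7 adds a check before the participant leaves: "A participant should not be released from the study center until the results of C-SSRS are reviewed". Treatment-emergent suicidal behaviour is an event of special interest reportable within 24 hours, so the sponsor may hear of a case quickly. Some participants reporting behaviour would also report Type 4 or 5 ideation and be excluded automatically. For direct rollovers, Visit 1 coincides with lead-in Visit 7, and the lead-in study may have its own C-SSRS rule.

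Most of this stands, and it limits the weight of the point. It does not remove it. Every route listed, apart from the overlap with Type 4 or 5 ideation, is either a risk assessment or a reporting duty. Even on the narrower reading of the first limb, someone must decide that the self-harm risk is significant. An investigator-opinion clause also exists after entry, and the sponsor nevertheless made behaviour an automatic trigger at Visits 2 to 10. The same reasoning applies at the visit where drug is first given. A lead-in rule, if there is one, is not in these documents and would not be a rule of this protocol.

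**Conclusion.** The point holds. The compulsory C-SSRS clause at entry omits all four positive behaviour types that compel withdrawal at the next nine visits, and no other provision supplies an automatic rule at Visit 1. The gap lies in uniformity: judgement-based cover exists and should catch most cases.

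The size in participants cannot be derived from the documents. It is likely to be very small, because it requires behaviour reported at Visit 1, no concurrent Type 4 or 5 ideation, and an investigator who does not judge the risk significant. The trigger counts describe the wording and are not estimates of risk. No planned analysis is affected. The conclusion rests on the text of this protocol alone and assumes nothing about the lead-in study's own rules. The change is worth making because the signal is serious and the correction is cheap.

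**What to change.** In Protocol 4.3, criterion 5, insert *or any suicidal behavior on the C-SSRS* into the compulsory clause, after the reference to Type 4 or 5 and before the words on the recall period. The entry rule then has the same triggers as 6.5.7 and 8.9, in terms the protocol already uses.

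The cost is one clause. The behaviour section is already completed at Visit 1, so no assessment, visit or data field is added, and the SAP needs no change. The downside is that a very small number of rollover participants would be excluded by rule where an investigator might have judged them suitable.
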